
 
• Concordance between investigator's intra-operative conspicuity assessment of the ureter and BICR assessment for adults with normal renal function or mild renal impairment
 
	
 
• Intra-participant difference in ureter conspicuity for WL versus NIR-F at 30 (<math>\pm 15</math>) min after ASP5354 administration by each BICR reader
 
• CCC, the inter-rater reliability between the investigators and BICR for the WL versus NIR-F at 30 (<math>\pm 15</math>) min after ASP5354 administration
 
• Intra-participant difference in ureter conspicuity for WL at 30 (<math>\pm 15</math>) min versus the average of all NIR-F time points by each BICR reader
 
• CCC, the inter-rater reliability between the investigators and BICR for the WL at 30 (<math>\pm 15</math>) min time point versus the average of all NIR-F time points
 
• Intra-participant difference in ureter conspicuity for WL at 30 (<math>\pm 15</math>) min versus the
 

Objectives	Endpoints
	
end of surgery time point score with NIR-F by each BICR reader
 
 
CCC, the inter-rater reliability between the investigators and BICR for the WL 30 (<math>\pm</math> 15) min time point versus the end of surgery time point score with NIR-F
 

 
Safety of ASP5354
 
	
 
Nature, frequency, severity and causality of TEAEs and serious TEAEs
 
Clinical laboratory tests (hematology, biochemistry and urinalysis)
 
Vital signs
 
Electrocardiograms/cardiac monitoring
 

 
Investigate the pharmacokinetics of ASP5354
 
	
 
Plasma and urine concentrations of ASP5354
 
Ae and Ae%
 

Exploratory	

 
To summarize the investigator's conspicuity assessment with WL of the ureter at each time point
 
	
 
Descriptive summary of left and right ureter conspicuity scores for WL at each time point
 
Descriptive summary of index and non-index ureter conspicuity scores for WL at each time point
 

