2.3 Randomization

This study will enroll approximately 107 participants (84 adults with normal renal function or mild renal impairment [$eGFR \geq 60 \text{ mL/min}$], up to 10 adults with moderate or severe renal impairment [$eGFR \geq 15 \text{ to } < 60 \text{ mL/min}$] and 13 adolescents with normal renal function or mild renal impairment [$eGFR \geq 60 \text{ mL/min}$]) who will receive a single intravenous 3 mg dose of ASP5354. The normal/mild eGFR cohort will be randomized to 2 arms: WL/NIR-F and WL-only. Randomization will be stratified by type of surgery, (i.e., gynecological; other abdominopelvic). Details will be specified in the study randomization specification document, including allocation ratio, etc. There is no randomization for adult participants in the moderate/severe eGFR cohort or adolescent participants, and all of these participants will be evaluated with WL/NIR-F.

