3 SAMPLE SIZE

Only adult participants with normal renal function/mild renal impairment randomized to WL/NIR-F will be included in the analysis of the primary and key secondary endpoints. Adolescent participants and participants with moderate/severe renal impairment will be included in other secondary analyses. Screen failures and participants who are not randomized or enrolled will not be evaluated.

Normal/Mild eGFR Cohort (Participants ≥ 18 years of age)

The sample size calculation is based on the primary efficacy endpoint. When assuming the difference in the score of the ureter conspicuity under NIR-F compared with WL is 1.0 with a common standard deviation of 2.0 and the correlation is 0.2, 84 adult participants randomized to either WL/NIR-F or WL-only at the selected allocation ratio will provide enough participants in the WL/NIR-F arm for 90% power to demonstrate a statistically significant difference from 0 at a 2-sided significance level of 0.05 using the paired t-test.

Moderate/Severe eGFR Cohort (Participants ≥ 18 years of age)

Up to 10 participants with moderate or severe renal impairment ($eGFR: 15 \text{ to } < 60 \text{ mL/min}$) will be enrolled into the WL/NIR-F arm and receive ASP5354. All participants with moderate or severe renal impairment will be assessed with both WL and NIR-F during surgery (non-randomized cohort). In the event that enrollment of participants with normal renal function/mild renal impairment and adolescents is completed prior to enrolling 10 participants with moderate/severe renal impairment, enrollment of participants in the moderate/severe eGFR cohort will end. Therefore, the final number of participants with moderate/severe renal impairment will be between 0 and 10.

Adolescent Cohort (Participants \geq 12 and $<$ 18 years of age)

Approximately 13 adolescents with normal renal function or mild renal impairment (eGFR \geq 60 mL/min) will be enrolled and receive ASP5354 such that a minimum of 10 evaluable adolescent participants complete the study to allow collection of pharmacokinetic samples from at least 6 participants in age group \geq 12 and $<$ 15 years and at least 4 participants in age group \geq 15 and $<$ 18 years. All adolescent participants will be assessed with both WL and NIR-F during surgery (non-randomized cohort). Assuming approximately 20% of participants might not facilitate derivation of plasma pharmacokinetic parameters, 13 adolescent participants would need to be enrolled.

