The analysis of the additional secondary endpoints will be conducted using the following groups of participants. P-values and confidence intervals will not be presented. This analysis will be performed after applying the ICE1 and ICE2 imputation as well as the visit windowing algorithm described in section [6.8.1](#).

- Adolescents
- Adults with moderate renal impairment (eGFR ≥ 30 to < 60 mL/min)
- Adults with severe renal impairment (eGFR ≥ 15 to < 30 mL/min)

To further characterize the difference of ureter conspicuity under NIR-F vs WL, the frequency and percentage of participants with an averaged ureter conspicuity assessed by the investigator over all NIR-F time points during surgery at least 1 point higher than the average ureter conspicuity over all WL time points during surgery will be presented. The same analysis will be repeated using a difference of 2, 3 and 4 points. The frequency and percentage of participants with an averaged ureter conspicuity within NIR-F during surgery at least 1 point higher than their WL conspicuity at the 30-min time point during surgery will be presented. The analysis will also be repeated using a difference of at least 2, 3 and 4 points.

The qualitative assessment of index ureter(s) conspicuity scored on a 5-point Likert Scale under WL and NIR-F (1 = None, 2 = Poor, 3 = Sufficient, 4 = Good and 5 = Excellent) performed by a BICR will be summarized descriptively at all time points post-ASP5354 administration by WL and NIR-F for each separate BICR reader. The descriptive analysis of the primary and key secondary endpoints will be repeated for each separate BICR reader. This analysis will be conducted within adolescents, adults with moderate renal impairment, adults with severe renal impairment, the ITT population and the mITT population. The BICR data will be assigned to the same analysis time points as the corresponding investigator assessments. The same ICE1 and ICE2 imputation will also be applied within the BICR data. In the event that a BICR assessment cannot be collected for a corresponding investigator assessment, the corresponding analysis time point will be considered missing in the BICR analysis. If a backup reader is utilized in place of a primary reader, the primary reader and their backup will be considered the same BICR reader in the analysis.

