The concordance analysis between BICR readers and investigators will be conducted for the ITT population. The hypothesis testing for the primary and key secondary endpoints will be repeated for each separate BICR reader. This will be the primary measure of concordance between the BICR readers and investigator data. A high concordance between the two assessments is considered if 2 of 3 BICR readers yield p-value ≤ 0.05 .

The CCC measuring the agreement between investigator and BICR Likert conspicuity scores will be presented for the following values for each separate BICR reader for the ITT population. This is considered a secondary measure of reliability compared to the hypothesis testing as differences between the raw conspicuity scores of the BICR readers and investigator data may be expected due to the different environments under which conspicuity is assessed.

- Difference between NIR-F and WL at the 30-min time point
- Mean difference between NIR-F across all time points and WL at the 30-min time point
- Difference between NIR-F at the end of surgery time point and WL at the 30-min time point

In addition to the CCC, Kendall's coefficient of concordance along with 95% jackknife CI will be presented in order to assess the agreement across all raters.

BICR data will be listed.

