6.4.5 Other Efficacy Analysis

All analyses of the 5-Point Likert Scale for conspicuity and CEF will be conducted using conspicuity assessments mapped to time points using the windowing algorithm described in Section 6.8.1.

Subgroup analysis will be conducted on the primary endpoint, key secondary endpoints and color contrast quantitative assessment (CEF) within the ITT population. Data imputation described in the analysis of the primary and key secondary endpoints will also be applied to the subgroup analysis.

The endpoints listed above will be summarized using descriptive statistics within the following subgroups:

- BMI (underweight or normal, $<25 \text{ kg/m}^2$; overweight, ≥ 25 to $<30 \text{ kg/m}^2$; obese, $\geq 30 \text{ kg/m}^2$)
- Prior pelvic or abdominal surgery (yes; no)
- Prior inflammatory disorder (yes; no)
- Type of surgery (gynecological; other abdominopelvic)
- Type of surgery (minimally invasive only; open only; minimally invasive and open)
- Type of device (1688; SPY-PHI; Other)
- Sex (female; male)
- EudraCT Age (≥ 12 and <18 ; ≥ 18 and <65 ; ≥ 65 to <85 ; ≥ 85)
- Ethnicity (Hispanic or Latino; Not Hispanic or Latino)
- Race (American Indian or Alaska Native; Asian; Black or African American; Native Hawaiian or Other Pacific Islander)

Summaries by surgeon will also be presented.

Further, the following analyses of conspicuity data will only use observed records mapped to time points using the windowing algorithm but will not have data imputation applied.

The descriptive summaries of the primary end point, key secondary endpoints and CEF will be repeated using data collected from non-index ureters on participants in the ITT population.

Descriptive statistics for the number of NIR-F conspicuity time points for each participant during surgery will be presented.

Descriptive statistics for WL and NIR-F conspicuity scores will be presented by time point for the ITT and mITT populations. A line chart displaying the NIR-F and WL scores by time point will be provided for the mITT population.

The frequency and percentage of participants with each WL and NIR-F conspicuity score will be presented by time point for the ITT and mITT populations. This will be repeated for the non-index ureter for the ITT population.

The frequency and percentage participants who experience ICES throughout the study will be presented for the ITT and mITT populations. The specific categories and subcategories will be as follows:

- Any ICE
- ICE1 Total

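### Participants whose NIR-F minus WL difference is set to 0 by ICE1 or by the ICE2 fallback rules count as investigator–BICR agreement in the CCC and Kendall's coefficient

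*SAP*

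**What the plan says.** Agreement between investigator and BICR is a named secondary endpoint. Protocol Table 4 lists "CCC, the inter-rater reliability between the investigators and BICR for the WL versus NIR-F at 30" min, with matching CCCs for the average over all NIR-F time points and for the end of surgery.

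SAP 6.4.3 says of the reader scores: "The same ICE1 and ICE2 imputation will also be applied within the BICR data". Later in the same section: "The CCC measuring the agreement between investigator and BICR Likert conspicuity scores will be presented", per reader in the ITT population, for three NIR-F minus WL differences. Kendall's coefficient across all raters is added. Neither statistic is restricted to observed scores. SAP 6.4.5 names a set of analyses that "will only use observed records mapped to time points using the windowing algorithm but will not have data imputation applied"; the CCC and Kendall's coefficient are not in it.

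The imputation rules are in SAP 5.1, 6.4.1.1 and 6.4.2:

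- ICE1: both 30-min scores become 1. After ICE1, NIR-F scores at later time points are replaced by the 30-min WL score.
- ICE2, late first assessment: the earliest score obtained in that light mode stands in for the 30-min score.
- ICE2, one mode never assessed: its 30-min score is copied from the other mode.
- ICE2, nothing assessed: both 30-min scores become 1.

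If a BICR read cannot be obtained for an existing investigator score, SAP 6.4.3 leaves it missing.

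**The concern.** An agreement statistic asks whether raters who looked at the same ureter gave the same result. A failure value is reasonable in an effect test, where a zero difference works against the product. In an agreement statistic the same zero, given to the investigator and to every reader, is a perfectly concordant pair, and it works in favour of the product.

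The BICR is the design's independent check on the investigator's score. SAP 6.4.3 takes as its main concordance criterion that 2 of 3 readers reach p ≤ 0.05. That shows that the readers also see an effect, not that their scores match the investigator's. The CCC and Kendall's coefficient are therefore the only planned statistics that measure investigator–BICR agreement directly.

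The plan itself expects the triggering cases to be possible. SAP 6.4.5 tabulates ureteral stents and participants with no conspicuity assessment, and SAP 6.4.1.2 adds an analysis for randomized participants who were not dosed and who stay in the ITT set.

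**Working it through.** **Planning figure.** The documents give no CCC value, CCC target or ICE rate. The nearest figure is the sample size: the difference "is 1.0 with a common standard deviation of 2.0 and the correlation is 0.2", with "84 adult participants randomized to either WL/NIR-F or WL-only at the selected allocation ratio" giving "90% power to demonstrate a statistically significant difference from 0 at a 2-sided significance level of 0.05 using the paired t-test". The SD of the difference is 2.0 × √(2 × (1 − 0.2)) = 2.53. A paired t-test then needs 70 in the WL/NIR-F arm (power 90.3%). From 84 randomized, 4:1 gives 67 (89.0%), 5:1 gives 70 (90.3%) and 2:1 gives 56 (82.8%). The ratio is not in the documents ("Details will be specified in the study randomization specification document, including allocation ratio, etc"), so the figure cannot be fully reproduced. It serves here only to set n = 70 in the simulation of step 4.

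**Step 1. Which rules force a zero for every rater?**

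| Rule | 30-min NIR-F − WL | Forced agreement? |
|---|---|---|
| ICE1 before the 30-min assessment | 1 − 1 = 0 | Yes |
| ICE1 after it | unchanged under SAP 5.1; 0 at the later time points affected | At those time points only |
| ICE2, late first assessment | each rater's own scores | No |
| ICE2, one mode never assessed | copied, so 0 | Yes |
| ICE2, nothing assessed | 1 − 1 = 0 | Yes |

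SAP 5.1 limits the 30-min overwrite to ICE1 that occurs before that assessment. SAP 6.4.1.1 does not carry that limit. Read literally, it would also overwrite genuine 30-min scores after a late ICE1 and create more zero pairs.

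**Step 2. Effect on the CCC.** For raters x and y with means m and SDs s among observed pairs:

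CCC = 2·s_xy / D, with D = s_x² + s_y² + (m_x − m_y)².

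If a share p of all pairs is (0, 0):

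1 − CCC_imputed = (1 − CCC_observed) × D / (D + 2·p·m_x·m_y).

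A numerical check gave 0.6063 both ways. The CCC therefore rises whenever m_x and m_y have the same sign and the observed CCC is below 1.

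**Step 3. Size.** Take an observed CCC of 0.20 and the same mean and SD for both raters. The ICE share is an assumption throughout.

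| Mean, SD of difference | 2% | 5% | 10% | 20% |
|---|---|---|---|---|
| 1.0, 2.53 (planning) | 0.202 | 0.206 | 0.212 | 0.224 |
| 2.0, 1.2 (assumed) | 0.242 | 0.298 | 0.374 | 0.486 |
| 2.5, 1.0 (assumed) | 0.289 | 0.390 | 0.508 | 0.644 |

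Worked cell (2.5, 1.0, 10%): D = 1 + 1 = 2; 2 × 0.10 × 2.5 × 2.5 = 1.25; 1 − 0.80 × 2/3.25 = 0.508. With no real agreement at all, the same setting gives 1 − 2/3.25 = 0.385. An SD of 2.0 is the most that a 1–5 score can have (half the scores at each end), so the planning row probably understates the effect.

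**Step 4. Kendall's coefficient.** This was simulated with n = 70, four raters, scores rounded to 1–5, and 7 of 70 imputed. With mean difference about 2.2 and SD 1.2 it rises from 0.43 to 0.57. With mean about 0.7 and SD 1.9 it rises only from 0.44 to 0.46.

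**The case against.** Much can be said for the plan. The CCC paragraph does not itself say that imputed values are used; that is read from the BICR imputation sentence and the absence of an exemption in SAP 6.4.5. ICE1 should be uncommon, because anticipated stenting is excluded and ICG and other NIR-F agents are restricted. If no ITT participant is zero-imputed, there is no bias. SAP 6.4.3 ranks the CCC as a secondary measure of reliability, and it has no threshold. ICE counts and listings of all scores are planned, so a reader of the report could see part of the effect. All of this stands and limits the consequence. It does not remove the rule: SAP 6.8 and 6.8.1 state the imputation generally for Likert data, so a programmer following the SAP would feed imputed values into both statistics.

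Four stronger readings are tempting and are not supported:

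- That all ICE2 imputation manufactures agreement. The late-assessment rule uses each rater's own scores.
- That every ICE1 participant is a zero pair throughout. Under SAP 5.1, ICE1 after the 30-min assessment leaves the 30-min CCC untouched, and the average over time points still contains real earlier scores.
- That the main concordance conclusion is inflated. In the repeated tests the zeros pull the mean difference towards 0.
- That the ICCs are equally affected. SAP 6.4.4 defines them on image reads and repeat reads and does not say that imputed values enter; this needs a clarifying sentence only.

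**Conclusion.** The concern holds in a limited form. As written, ICE1 and the two ICE2 fallback rules put pairs into the CCC and Kendall's coefficient that agree by construction. The direction for the CCC is certain, given at least one such participant and positive mean differences for both raters, which is what the trial expects. The size cannot be settled from the documents. At 10% imputed, from an observed 0.20, the rise is about 0.01 at the planning values, 0.17 at mean 2.0 and SD 1.2, and 0.31 at mean 2.5 and SD 1.0. It rests on an assumed ICE share and, beyond the planning row, on assumed means and SDs. What is at risk is the reported level of investigator–BICR agreement, not the primary result or the 2-of-3-readers criterion.

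**What to change.** In SAP 6.4.3, compute the CCC and Kendall's coefficient only on participants and time points where the investigator and the reader or readers each have an actual score. Exclude values set by ICE1 and by the two ICE2 fallback rules. Also exclude scores taken after ICE1, which SAP 5.1 treats as not relevant. Keep the rule that uses the earliest actual score when the first assessment is late, since those are genuine paired reads. A blanket removal of imputation would lose those pairs and could let post-ICE1 scores back in. Report the number of pairs used and excluded for each coefficient.

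In SAP 6.4.4, state that the inter- and intra-rater ICCs use actual image reads only. Reconcile SAP 5.1 with 6.4.1.1 on whether ICE1 after the 30-min assessment overwrites the 30-min scores. Keep the imputation for the repeated primary and key secondary tests.

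The cost is a few sentences and a data-selection flag. The downside is slightly fewer pairs and probably a lower reported coefficient.

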5.4 Exploratory Efficacy Endpoints

The exploratory efficacy endpoints are as follows:

- Descriptive summary of left and right ureter conspicuity scores for WL at each time point
- Descriptive summary of index and non-index ureter conspicuity scores for WL at each time point
- Intraclass correlation coefficient (ICC), the inter-rater reliability among BICR readers on the intra-participant difference in ureter conspicuity for WL versus NIR-F at 30 (± 15) after ASP5354 administration
- ICC, the inter-rater reliability among BICR readers on the scoring in ureter conspicuity for the WL and NIR-F at 30 (± 15) min after ASP5354 administration

- ICC, the intra-rater reliability within each BICR reader on the intra-participant difference in ureter conspicuity for WL versus NIR-F at 30 (± 15) min after ASP5354 administration
- ICC, the intra-rater reliability within each BICR reader on the scoring in ureter conspicuity for the WL and NIR-F at 30 (± 15) min after ASP5354 administration

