In analyses of BICR data where BICR readers assess the same 30-min image twice, the second reading will only be used in the analysis of intra-rater reliability within BICR readers. In other analyses of BICR data, only the first assessment will be analyzed.

All safety summaries will be presented for the following groups unless otherwise specified:

- All participants who received ASP5354
- Adult participants (≥ 18 years)
- Adult participants randomized to the WL/NIR-F arm
- Adult participants randomized to the WL-only arm
- Adult and adolescent participants enrolled/randomized to the WL/NIR-F arm
- Adolescent participants (12 to < 18 years)
- Participants with moderate renal impairment (eGFR ≥ 30 to < 60 mL/min)
- Participants with severe renal impairment (eGFR ≥ 15 to < 30 mL/min)

For participants who re-screen and have a new participant ID assigned, only data collected under the new participant ID will be used in the analysis. Data collected under the old participant ID will be listed only.

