6.4.4 Analysis of Exploratory Efficacy Endpoints

The exploratory efficacy endpoints are listed in section [5.4](#).

Descriptive statistics will be used to summarize the ureter conspicuity by time point under WL for both the left and right ureters of participants in the ITT and mITT population. In addition, the same descriptive statistics summary will be applied for the ureter conspicuity under WL for both index and non-index ureters in the ITT and mITT populations.

Inter- and intra-rater reliability within the BICR readers will be measured using the assessments at the 30-min time point for the ITT population and will be assessed using an ICC with a 95% CI. Inter-rater reliability of the differences between the 30-min WL and 30-min NIR-F values as well as the raw values under WL and NIR-F will be assessed. Intra-rater reliability of the repeat readings of the 30-min WL and 30-min NIR-F images will also be assessed. Intra-rater reliability of the differences between the 30-min WL and 30-min NIR-F values will also be assessed. ICC will be calculated using Shrout-Fleiss formulae for estimation of inter- and intra-rater reliability (agreement) (ICC [2, 1], as defined in Qin et al., 2019). As a primary indicator, ICC for inter-rater and intra-rater (also called test-retest) reliability will be assessed using separate ANOVA models. Inter-rater reliability will be assessed using a random-effects ANOVA, estimating random effects of BICR reader and image. Intra-rater reliability will be assessed using a mixed-effect ANOVA, estimating random effects of BICR reader, image and fixed effect of time point. Parameters from the outputs obtained in these analyses will be used in the formula below to calculate two ICCs (for inter-and intra-rater reliability):

$$\frac{MS_B - MS_E}{MS_B + (k - 1)MS_E + k/n(MS_W - MS_E)}$$

where MS_B = mean squares for image (for inter-rater reliability), MS_E = mean square for error, n = number of images (for inter-rater reliability), k = number of surgeon raters (for inter-rater reliability), and MS_W = mean square for rater (for inter-rater reliability).

In the case of intra-rater reliability, the above formula has a slightly different interpretation: MS_W = mean square for time point and k = number of time points (here 2) and n = number of raters multiplied by the number of images.

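### The SAP counts a replaced BICR reader and the backup as one reader without exception, so a repeat reading by a different person would be reported as intra-rater reliability

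*SAP*

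**What the plan says.** **Merge rule.** SAP 6.4.3 covers substitution among the central readers: "If a backup reader is utilized in place of a primary reader", then "the primary reader and their backup will be considered the same BICR reader in the analysis". The rule carries no exception and does not say whether the backup takes over the remaining images or re-reads all of them.

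**Intra-rater reliability.** SAP 6.1 deals with 30-min images that are read twice: "the second reading will only be used in the analysis of intra-rater reliability within BICR readers". The exploratory endpoints in SAP 5.4 are "the intra-rater reliability within each BICR reader on the scoring in ureter conspicuity" and "ICC, the intra-rater reliability within each BICR reader on the intra-participant difference in ureter conspicuity for WL versus NIR-F". SAP 6.4.4 adds: "Intra-rater reliability of the repeat readings of the 30-min WL and 30-min NIR-F images will also be assessed". Its ICC formula for this case takes "k = number of time points (here 2) and n = number of raters multiplied by the number of images".

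**Per-reader effect.** SAP 6.4.3 also says: "The hypothesis testing for the primary and key secondary endpoints will be repeated for each separate BICR reader". High concordance is declared if two of three readers reach p ≤ 0.05.

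**Reading procedure.** Protocol 7.1.5 has WL and NIR-F images prepared separately and shown to readers in random order. Protocol 10.1.6.1 leaves reader training and replacement to a charter that is not in the documents.

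**The concern.** Test-retest reliability requires the same person on both occasions. If one surgeon makes the first reading and another the repeat, the pair measures inter-rater agreement. The merge rule would still give both readings one reader label. The SAP 6.4.4 model has terms for reader, image and time point but none for the individual behind a merged label, so it cannot separate the two kinds of pair.

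At stake is the meaning of an exploratory figure. The central review supports an investigator who knows the illumination mode, and the intra-rater ICC is what shows whether a central reader is consistent with himself or herself. A figure mixed with between-person pairs does not answer that question.

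**Working it through.** The plan states no expected ICC, replacement rate or BICR sample size, so there is no plan figure to reproduce. The check is first textual, then illustrative.

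**1. Does the rule reach the intra-rater ICC?** The rule is in SAP 6.4.3 and the ICC in 6.4.4. The rule applies to the analysis without restriction, and 6.4.4 gives no other definition of a reader. SAP 5.4, 6.1 and 6.4.4 contain no condition that both readings come from one individual. On the text, split repeats would be included.

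**2. How many repeats could be split?** Assume first and repeat readings are mixed in one random order, and the primary reader completes a share p of them before the backup takes over. The share of split repeat pairs is f = 2p(1 − p).
- p = 0.5: f = 2 × 0.5 × 0.5 = 50%, the maximum.
- p ≈ 0.89: f = 2 × 0.89 × 0.11 ≈ 20%.

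A larger f would need the repeats to be read in a separate later session by the backup, which no section describes.

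**3. ICC for the affected slot.** Assume agreement of 0.85 within a person and 0.60 between people. To a good approximation, ICC = 0.85 − (0.85 − 0.60) × f.
- f = 20%: 0.85 − 0.25 × 0.20 = 0.80.
- f = 50%: 0.85 − 0.25 × 0.50 = 0.725, about 0.73.

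**4. ICC pooled over readers.** SAP 6.4.4 sets n to raters times images, which pools the readers. With one of three slots affected, taking a simple average:
- f = 20%: (0.80 + 0.85 + 0.85) / 3 = 0.83.
- f = 50%: (0.725 + 0.85 + 0.85) / 3 = 0.81.

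SAP 5.4 speaks of each reader, so a per-reader figure could also be reported. Both are therefore shown.

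**5. Cross-check by simulation with the SAP 6.4.4 formula.** Assumptions for one slot: 140 images (70 participants × 2 modes), true image SD 1.2, repeat-read SD 0.5, reader-by-image SD 0.5 to 0.8, backup offset 0.5 to 1.0 point, scores rounded to 1–5.

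| Split repeats | ICC, affected slot |
|---|---|
| 0% | 0.82–0.84 |
| 10% | 0.79–0.81 |
| 25% | 0.74–0.78 |
| 50% | 0.67–0.73 |

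The direction is the same as in step 3: splits lower the ICC.

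**6. Per-reader NIR-F minus WL differences.** Let b be the gap between the two people's use of the scale. In random order, WL by the primary with NIR-F by the backup is as likely as the reverse, each with probability p(1 − p). The mean shift is b·p(1 − p) − b·p(1 − p) = 0, and the variance rises by f·b². The design values in Protocol 9.5.1.1 (difference 1.0, SD 2.0, correlation 0.2) give an SD of the difference of √(2 × 2.0² × 0.8) = 2.530. Assume n = 70 in the WL/NIR-F arm, which is 84 × 5/6 at a 5:1 allocation; the documents do not state the ratio.

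| Case | SD | Per-reader power |
|---|---|---|
| No split | 2.530 | 90.3% |
| f = 25%, b = 0.5 | 2.542 | 90.1% |
| f = 50%, b = 0.5 | 2.554 | 89.8% |
| f = 25%, b = 1.0 | 2.579 | 89.2% |
| f = 50%, b = 1.0 | 2.627 | 88.1% |

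Setting split differences to missing instead would leave n = 35 at f = 50%, with power of about 62%.

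**The case against.** The strongest objection is that the merge rule splits nothing by itself. Whether a backup finishes a partly read set, takes whole participants or re-reads everything belongs to the charter. If the backup re-reads the full set, the rule is harmless. That is correct, and it makes the point conditional. It does not remove it, because the SAP neither states such a condition nor refers to the charter for one.

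It can also be said that split repeats make the central readers look less consistent, not more, and that pooling over readers dilutes the effect. Both statements stand, and they keep the point small.

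A reader might infer something stronger: that the merge also undermines the per-reader NIR-F minus WL tests and the 2-of-3 rule, because a participant's WL and NIR-F images could be scored by different people. The documents do not support that. With random reading order a constant scale gap roughly cancels in the mean, and the remaining noise costs about 2 percentage points of power at most in the cases above. A one-directional shift (f × b, for example 0.25 × 1.0 = 0.25 point) would need a takeover that follows illumination mode. Protocol 7.1.5 does not say whether the two modes are mixed in one sequence, but no section describes a takeover of that kind. The merged slot also has a clear purpose: it keeps three complete readers for the 2-of-3 criterion.

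**Conclusion.** The point holds for the intra-rater ICC only. As written, the SAP would report any repeat reading made by a different person as within-reader agreement, contrary to the endpoint in SAP 5.4. It matters only if a backup takes over part of the reads. In that case the bias would usually be downward: on assumed agreement of 0.85 and 0.60, to about 0.80 (20% split) or 0.73 (50% split) for the affected slot, and to about 0.83 or 0.81 pooled over three readers. These agreement values are assumptions. The simulation, which uses other assumed inputs, shows a similar pattern.

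The consequence is limited to an exploratory analysis. The investigator-based primary and key secondary tests are untouched, and the per-reader tests and the CCC can keep the merged slot. This is a useful clarification, not a defect that threatens a main conclusion.

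**What to change.** Keep the merged reader slot for descriptive summaries, per-reader tests, the CCC and the 2-of-3 rule. Add to SAP 6.4.3 and 6.4.4:

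> *For intra-rater reliability, only image pairs with both readings by the same individual, identified by individual reader ID, will be used. For the intra-rater ICC of the WL versus NIR-F difference, all readings entering the pair must be by the same individual.*

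Report the number of split repeats and of split WL/NIR-F pairs. If any occur, add a sensitivity analysis of the per-reader differences that excludes split pairs. Do not set them to missing in the main analysis, given the power loss in step 6.

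**Cost:** SAP wording and an individual reader ID in the BICR dataset. Some repeat pairs drop out of the exploratory ICC if a reader is replaced midway. In the worst case of step 2 (p = 0.5), half of that slot's single-image repeats would remain. For the difference ICC, which needs four readings by one person, 0.5⁴ + 0.5⁴ = 12.5% would remain, so for that slot it may be too sparse to interpret and should be shown with its count. If the charter already prevents split reads, the added text changes no result and puts that fact on record.
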